6.6.3.6. Dose Delays

Applicable to PF-07901801 and tafasitamab.

Dose Delay is the difference between the actual time between two consecutive non-zero doses and the planned time between the same two consecutive non-zero doses.

Dose Delay for Dose x (days) = Date of Dose x – Date of Dose (x-1) – Planned days between two consecutive doses.

Dose delays will be grouped into the following categories:

- No delay
- 1-2 days delay
- 3-6 days delay
- 7 or more days delay

For example, for PF-07901801, administered on a 2-week schedule, if one patient receives avelumab on Day 1, then the next PF-07901801 administration date will be on Day 15; however, if the patient receives PF-07901801 at Day 16 or 17, this is considered as 1-2 days delay.

No delay and 1-2 days delay will also be summarized together.

The number and percentage of patients with delayed study drug administration and maximum length of delay, ie, the worst case of delay if patients have multiple dose delays will be summarized.

6.6.3.7. Infusion rate reductions

Applicable to PF-07901801.

The number and percentage of patients with at least one infusion rate reduction of $\geq 50\%$ compared to the first infusion rate reported in the eCRF as well as the frequency of patients with 1, 2, 3 or ≥ 4 infusion rate reductions of $\geq 50\%$ will be summarized.

6.6.3.8. Infusion interruptions

Applicable to PF-07901801

An infusion interruption is defined as an infusion that is stopped and re-started on the same day (ie, for a visit more than one infusion start time and infusion end time are recorded).

The number and percentage of patients with at least one infusion interruption as well as the frequency of patients with 1, 2, 3, or ≥ 4 infusion interruptions will be summarized.

6.6.4. Concomitant Medications and Nondrug Treatments

The following analyses will be based on the Safety Analysis Set.

Concomitant medications are medications, other than study medications, which started prior to first dose date of study treatment and continued on on-treatment period as well as those started during the on-treatment period. Prior medications are medications, other than study medications and pre-medications for study drug, which are started before the first dose of study treatment.

Prior and concomitant medications will be summarized from the 'Concomitant Medications' eCRF page. Pre-medications for study drug will also be summarized separately.

Summary of prior and concomitant medications will include the number and percentage of patients by Anatomical Therapeutic Chemical (ATC) Classification level 2 and preferred term. A patient will be counted only once within a given drug class and within a given drug name, even if he/she received the same medication at different times. If any prior or concomitant medication is classified into multiple ATC classes, the medication will be summarized separately under each of these ATC classes. The summary tables will be sorted on decreasing frequency of drug class and decreasing frequency of drug name in a given drug

class. In case of equal frequency regarding drug class (respectively drug name), alphabetical order will be used. In case any specific medication does not have ATC classification level 2 coded term, it will be summarized under 'Unavailable ATC classification' category.

A listing of concomitant medications will be created with the relevant information collected on the 'Concomitant Medications' eCRF page.

A listing of concurrent procedures will be created with the relevant information collected on the 'Non-drug Treatments' eCRF page.

6.6.5. Subsequent Anti-Cancer Therapies

The following analyses will be based on the Safety Analysis Set by treatment group for Phase 1b and Phase 2 separately.

Anti-cancer treatment will be provided in a data listing with data retrieved from 'Follow-up Cancer Therapy', 'Radiation', and 'Cancer Surgery' eCRF pages.

Number and percentage of patients with any anti-cancer therapy after discontinuation will be tabulated overall and by type of therapy based on the data collected from the 'Follow-up Cancer Therapy', 'Radiation' and 'Cancer Surgery' eCRF pages.

6.7. Safety Summaries and Analyses

Summaries of AEs and other safety parameters will be based on the Safety Analysis Set.

6.7.1. Adverse Events

Treatment-emergent adverse events (TEAEs) are those events with onset dates occurring during the on-treatment period for the first time, or if the worsening of an event is during the on-treatment period as defined in Section 5.2.7.

All analyses described below will be based on TEAEs if not otherwise specified. The AE listings will include all AEs (whether treatment-emergent or not). AEs outside the on-treatment period will be flagged in the listings. Summaries of TEAEs due to COVID-19 may be produced if appropriate.

- Related Adverse Events: adverse events with relationship to study treatment (as recorded on the AE eCRF page, Relationship with study treatment = Related) reported by the investigator and those of unknown relationship (i.e., no answer to the question 'Relationship with study treatment'). Related AEs are those related to any study drug (ie, at least one of the study drugs).
- Serious Adverse Events (SAE): serious adverse events (as recorded on the AE eCRF page, Serious Adverse Event = Yes).
- Adverse Events Leading to Dose Reduction: adverse events leading to dose reduction of study treatment (as recorded on the AE eCRF page, Action taken with study treatment = Dose reduced).

- Adverse Events Leading to Interruption of Study Treatment: adverse events leading to interruption of study treatment (as recorded on the AE eCRF page, Action taken with study treatment = Drug interrupted).
- Adverse Events Leading to Permanent Treatment Discontinuation: adverse events leading to permanent discontinuation of study treatment (as recorded on the AE eCRF page, Action taken with study treatment = Drug withdrawn).
- Adverse Events Leading to Death: adverse event leading to death (as recorded on the AE eCRF page, Outcome = Fatal, as well as AEs of Grade 5).

Unless otherwise specified, AEs will be summarized by number and percentage of patients with the AE in the category of interest as described above, by treatment group, primary SOC and PT.

Each patient will be counted only once within each SOC or PT. If a patient experiences more than one AE within a SOC or PT for the same summary period, only the AE with the strongest relationship or the worst severity, as appropriate, will be included in the summaries of relationship and severity.

6.7.1.1. All Adverse Events

Adverse events will be summarized by worst severity (according to NCI CTCAE version 5.0) per patient, using the latest version of MedDRA preferred term (PT) as event category and MedDRA primary system organ class (SOC) body term as Body System category.

In case a patient has events with missing and non-missing grades, the maximum of the nonmissing grades will be displayed. No imputation of missing grades will be performed.

The following tables will be created:

- The overall summary of AEs table will include the frequency (number and percentage) of patients with each of the following by treatment group:
 - TEAEs
 - TEAEs, Grade ≥ 3
 - Related TEAEs
 - Related TEAEs, Grade ≥ 3
 - TEAEs leading to dose reduction of PF-07901801
 - TEAEs leading to dose reduction of lenalidomide
 - TEAEs leading to interruption of PF-07901801

- TEAEs leading to interruption of tafasitamab
- TEAEs leading to interruption of lenalidomide
- TEAEs leading to discontinuation of PF-07901801
- TEAEs leading to discontinuation of tafasitamab
- TEAEs leading to discontinuation of lenalidomide
- TEAEs leading to discontinuation of all study drugs
- Related TEAEs leading to discontinuation of PF-07901801
- Related TEAEs leading to discontinuation of tafasitamab
- Related TEAEs leading to discontinuation of lenalidomide
- Related TEAEs leading to discontinuation of all study drugs
- Serious TEAEs
- Related Serious TEAEs
- TEAEs leading to death
- Related TEAEs leading to death

- TEAEs by SOC and PT and worst grade
- TEAEs related to PF-07901801 by SOC and PT and worst grade
- TEAEs related to tafasitamab by SOC and PT and worst grade
- TEAEs related to lenalidomide by SOC and PT and worst grade
- TEAEs leading to death by SOC and PT
- Related TEAEs leading to death by SOC and PT

6.7.1.2. Adverse events leading to dose reduction of study drug

AEs leading to dose reduction will be defined as AEs identified in the AE eCRF page with an action taken with study treatment of 'dose reduced'.

The frequency (number and percentage) of patients with each of the following will be presented for TEAEs leading to dose reduction of each study drug by treatment group:

- TEAEs leading to dose reduction of PF-07901801 by SOC and PT

- TEAEs leading to dose reduction of Tafasitamab by SOC and PT
- TEAEs leading to dose reduction of Lenalidomide by SOC and PT

The listing of all AEs leading to dose reduction will also be provided with the relevant information.

6.7.1.3. Adverse events leading to interruption of study drug

AEs leading to interruption will be defined as AEs identified in the AE eCRF page with an action taken with study treatment of 'drug interrupted'.

The frequency (number and percentage) of patients with each of the following will be presented for TEAEs leading to interruption of each study drug by treatment group:

- TEAEs leading to interruption of PF-07901801 by SOC and PT
- TEAEs leading to interruption of Tafasitamab by SOC and PT
- TEAEs leading to interruption of Lenalidomide by SOC and PT

The listing of all AEs leading to interruption of study treatment will also be provided with the relevant information.

6.7.1.4. Adverse events leading to discontinuation of study drug

The frequency (number and percentage) of patients with each of the following will be presented for TEAEs leading to permanent discontinuation of each study drug and study treatment, by treatment group:

- TEAEs leading to discontinuation of PF-07901801 by SOC and PT
- Related TEAEs leading to discontinuation of PF-07901801 by SOC and PT
- TEAEs leading to discontinuation of Tafasitamab by SOC and PT
- Related TEAEs leading to discontinuation of Tafasitamab by SOC and PT
- TEAEs leading to discontinuation of Lenalidomide by SOC and PT
- Related TEAEs leading to discontinuation of Lenalidomide by SOC and PT
- TEAEs leading to discontinuation of all study drugs by SOC and PT
- Related TEAEs leading to discontinuation of all study drugs by SOC and PT

The listing of all AEs leading to treatment discontinuation will also be provided with the relevant information.

6.7.2. Deaths

The frequency (number and percentage) of patients in the Safety Analysis Set who died at any time and who died within 28 days after last dose of study treatment as well as the primary reason for death, will be tabulated based on information from the 'Death Details' and 'Survival Follow-Up' eCRFs, by treatment group.

In addition, date and cause of death will be provided in individual patient data listing together with selected dosing information (study treatment received, date of first / last administration, dose) and will include the following information:

- AEs with fatal outcome (list preferred terms of AEs with outcome=Fatal, as well as AEs of Grade 5),
- Flag for death within 28 days of last dose of study treatment

Deaths due to COVID-19 may be presented in a separate listing if there is significant impact of COVID-19.

6.7.3. Serious Adverse Events

The frequency (number and percentage) of patients with each of the following will be presented for treatment-emergent SAEs by treatment group:

- SAEs by SOC and PT
- Related SAEs by SOC and PT

The listings of all SAEs will also be provided with the relevant information with a flag for SAEs with onset outside of the on-treatment period.

6.7.4. Laboratory Data

6.7.4.1. Hematology and Chemistry Parameters

Laboratory results will be classified according to the NCI CTCAE criteria version 5.0. Nonnumerical qualifiers (with the exception of fasting flags) will not be taken into consideration in the derivation of CTCAE criteria (e.g., hypokalemia Grade 1 and Grade 2 are only distinguished by a non-numerical qualifier and therefore Grade 2 will not be derived). Additional laboratory results that are not part of NCI CTCAE will be presented according to the categories: below normal limit, within normal limits and above normal limit (according to the laboratory normal ranges).

Quantitative data will be summarized using simple descriptive statistics (mean, SD, median, Q1, Q3, minimum, and maximum) of actual values and changes from baseline for each

nominal visit over time (unscheduled measurements would therefore not be included in these summaries as described in Section 5.2.9). End of Treatment visit laboratory results will be summarized separately. The changes computed will be the differences from baseline. Qualitative data based on reference ranges will be described according to the categories (i.e., Low, Normal, High).

Abnormalities classified according to NCI CTCAE toxicity grading version 5.0 will be described using the worst grade. For those parameters which are graded with two toxicities such as potassium (hypokalemia/hyperkalemia), the toxicities will be summarized separately. Low direction toxicity (e.g., hypokalemia) grades at baseline and post baseline will be set to 0 when the variables are derived for summarizing high direction toxicity (e.g., hyperkalemia), and vice versa.

For WBC differential counts (total neutrophil, lymphocyte, monocyte, eosinophil, and basophil counts), the absolute value will be used.

For calcium, CTCAE grading is based on Corrected Calcium and Ionized Calcium (C_{ALC10}). Corrected Calcium is calculated from Albumin and Calcium as follows:

$$\text{Corrected calcium (mmol/L)} = \text{measured total Calcium (mmol/L)} + 0.02 (40 - \text{serum albumin [g/L]}).$$

Liver function tests: Alanine aminotransferase (ALT), aspartate aminotransferase (AST), and total bilirubin (TBILI) are used to assess possible drug induced liver toxicity. The ratios of test result over upper limit of normal (ULN) will be calculated and classified for these three parameters during the on-treatment period.

Summary of liver function tests will include the following categories. The number and percentage of patients with each of the following during the on-treatment period will be summarized by treatment group:

- ALT $\geq 3 \times$ ULN, ALT $\geq 5 \times$ ULN, ALT $\geq 10 \times$ ULN, ALT $\geq 20 \times$ ULN
- AST $\geq 3 \times$ ULN, AST $\geq 5 \times$ ULN, AST $\geq 10 \times$ ULN, AST $\geq 20 \times$ ULN
- (ALT or AST) $\geq 3 \times$ ULN, (ALT or AST) $\geq 5 \times$ ULN, (ALT or AST) $\geq 10 \times$ ULN, (ALT or AST) $\geq 20 \times$ ULN
- TBILI $\geq 2 \times$ ULN
- Concurrent ALT $\geq 3 \times$ ULN and TBILI $\geq 2 \times$ ULN
- Concurrent AST $\geq 3 \times$ ULN and TBILI $\geq 2 \times$ ULN
- Concurrent (ALT or AST) $\geq 3 \times$ ULN and TBILI $\geq 2 \times$ ULN

- Concurrent (ALT or AST) $\geq 3 \times \text{ULN}$ and TBILI $\geq 2 \times \text{ULN}$ and ALP $> 2 \times \text{ULN}$
- Concurrent (ALT or AST) $\geq 3 \times \text{ULN}$ and TBILI $\geq 2 \times \text{ULN}$ and (ALP $\leq 2 \times \text{ULN}$ or missing)

Concurrent measurements are those occurring on the same date.

Categories will be cumulative, i.e., a patient with an elevation of AST $\geq 10 \times \text{ULN}$ will also appear in the categories $\geq 5 \times \text{ULN}$ and $\geq 3 \times \text{ULN}$. Liver function elevation and possible Hy's Law cases will be summarized using frequency counts and percentages.

An evaluation of Drug-Induced Serious Hepatotoxicity (eDISH) plot will also be created, with different symbols for different treatment groups, by graphically displaying

- peak serum ALT(/ULN) vs peak total bilirubin (/ULN) including reference lines at ALT= $3 \times \text{ULN}$ and total bilirubin = $2 \times \text{ULN}$.
- peak serum AST(/ULN) vs peak total bilirubin (/ULN) including reference lines at AST= $3 \times \text{ULN}$ and total bilirubin = $2 \times \text{ULN}$.

In addition, a listing of all TBILI, ALT, AST and ALP values for patients with a postbaseline TBILI $\geq 2 \times \text{ULN}$, ALT $\geq 3 \times \text{ULN}$ or AST $\geq 3 \times \text{ULN}$ will be provided.

Parameters with NCI-CTC grades available:

The laboratory toxicities will be tabulated using descriptive statistics (number of patients and percentages) during the on-treatment period. The denominator to calculate percentages for each laboratory parameter is the number of patients evaluable for CTCAE grading (i.e. those patients for whom a Grade 0, 1, 2, 3 or 4 can be derived).

- The summary of laboratory parameters by CTCAE grade table will include number and percentage of patients with Grade 1, 2, 3, 4, Grade 3/4 and any grade (Grades 1-4), laboratory abnormalities during the on-treatment period.
- The shift table will summarize baseline CTCAE grade versus the worst on-treatment CTCAE grade. The highest CTCAE grade during the on-treatment period is considered as the worst grade (Grade 0, 1, 2, 3, or 4) for the summary.

The above analyses apply to hematology and chemistry evaluations which can be graded per CTCAE, i.e.:

- **Hematology:**
Hemoglobin (HB), Leukocytes (white blood cell decreased), Lymphocytes (lymphocyte count increased/decreased), Neutrophils / Absolute Neutrophils Count (ANC) (neutrophil count decreased), Platelet Count (PLT) (platelet count decreased).

- Serum Chemistry:
Albumin (hypoalbuminemia), Alkaline Phosphatase (alkaline phosphatase increased), Alanine Aminotransferase (ALT) (ALT increased), Aspartate Aminotransferase (AST) (AST increased), Total Bilirubin (blood bilirubin increased, Creatinine (creatinine increased), Potassium (hypokalemia/ hyperkalemia), Sodium (hyponatremia/ hypernatremia), Magnesium (hypomagnesemia / hypermagnesemia), Calcium (hypocalcemia/ hypercalcemia), Glucose (hypoglycemia / hyperglycemia), Phosphates (hypophosphatemia).

Parameters with NCI-CTC grades not available:

Hematology and chemistry evaluations which cannot be graded per CTCAE criteria will be summarized as frequency (number and percentage) of patients with:

- shifts from baseline normal to at least one result above normal during on-treatment period
- shifts from baseline normal to at least one result below normal during on-treatment period

In this study, these apply to the following parameters:

- Hematology: Absolute Monocytes, Absolute Eosinophils, Absolute Basophils, and Reticulocytes
- Serum Chemistry: Chloride, Total Urea, Uric Acid, Lactate Dehydrogenase (LDH), Immunoglobulin

6.7.4.2. Other Laboratory Parameters

All other parameters collected on the eCRF will be listed in dedicated listings presenting all corresponding collected information on the eCRF.

- Coagulation: partial thromboplastin time (PTT) and prothrombin time (INR)
- Urinalysis: all urinalysis parameters
- Pregnancy test

The listings of laboratory results will be provided for all laboratory parameters. The listings will be sorted by parameters and assessment dates or visits for each patient. Laboratory values that are outside the normal range will also be flagged in the data listings, along with corresponding normal ranges. A listing of CTCAE grading will also be generated for those laboratory tests.

In addition, listings of abnormal values will be provided for hematology, chemistry, urinalysis, coagulation parameters. If there is at least one abnormal assessment for any parameter, all the data for that laboratory parameter will be included into the listing.

For all tests not mentioned above but present in the clinical data, a listing of patients with at least one result for the relevant test will be provided.

6.7.5. Vital Signs

Weight for the purposes of dose calculation will be recorded at screening and within 3 days pre-dose Day 1 of each cycle. Height will be measured at screening only.

Vital sign summaries will include all vital sign assessments from the on-treatment period. All vital sign assessments will be listed, and those collected outside the on-treatment period will be flagged in the listing.

All vital sign parameters will be summarized using descriptive statistics (mean, SD, median, Q1, Q3, minimum, and maximum) of actual values and changes from baseline for each visit over time. End of Treatment visit will be summarized separately. The changes computed will be the differences from baseline.

6.7.6. Electrocardiograms

ECG summaries will include all ECG assessments from the on-treatment period. All ECG assessment will be listed, and those collected outside the on-treatment period will be flagged in the listing.

QTcF will be summarized based on values collected on the eCRF. In case QTcF is missing, it will be derived based on RR and QT using the following formula:

$$QTcF = QT / \sqrt[3]{RR}$$

where RR represents the RR interval of the ECG, in seconds, and can be estimated as 60/Heart Rate.

If there are replicate measurements on the same nominal visit, the average of the replicate measurements will be reported and it should be determined after the derivation of the individual parameter at each time point.

ECG Summaries

The following analyses will be performed for each applicable ECG parameters (RR, PR, QT, QTcF and QRS) by treatment group, during the on-treatment period, for pre-PF-07901801 ECG records. The denominator to calculate percentages for each category is the number of patients evaluable for the category.

- For each of the ECG parameters (HR, QT, QTcF, QRS, PR intervals), descriptive statistics at baseline, at each post-baseline time point and changes from baseline at each post-baseline time point
- Frequency (number and percentage) of patients with notable ECG values according to the following categories:
 - QT/QTcF increase from baseline > 30 ms, > 60 ms
 - QT/QTc > 450 ms, > 480 ms, > 500 ms
 - HR ≤ 50 bpm and decrease from baseline ≥ 20 bpm
 - HR ≥ 120 bpm and increase from baseline ≥ 20 bpm
 - PR ≥ 220 ms and increase from baseline ≥ 20 ms
 - QRS ≥ 120 ms

For each of the ECG parameters, changes from pre-infusion to the end of infusion for PF-07901801 and changes from end of infusion for PF-07901801 to end of infusion for tafasitamab will also be summarized for the first 3 cycles.

Patients with notable ECG interval values and qualitative ECG abnormalities will be listed for each patient and time point and the corresponding notable values and abnormality findings will be included in the listings.

Unscheduled ECG measurements will not be used in computing the descriptive statistics for change from baseline at each post-baseline time point. However, they will be used in the analysis of notable ECG changes and the shift table analysis of notable QT parameters.

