**Table 1. Study Schedule of Assessment**

Visit Identifier	Screen	On-Treatment Period (28-day Cycle)												Notes			
		Cycle 1				Cycle 2-3				≥Cycle 4				EOT	FU visits		LTFU
Cycle Day	≤28d	D1	D4	D8	D15	D22	D1	D8	D15	D22	D1	D15	7d	28d	90d	Q12W	
 
Day relative to start of study intervention (Day 1).
 

Visit Window		(±1d)	(±2d)	(±2d)	(±2d)	(±2d)	(±2d)	(±2d)	(±2d)	(±2d)	(±2d)	(±2d)	(±2d post-last TX)	(28-35d post-last TX)	(+7 post-last TX)	(±14d post 90d FU)	
 
After 1 year of study intervention, cycle visit date windows are ±7d.
 

Vital signs	X	X	X	X	X	X	X	X	X	X	X	X	X	X			
 
On days of infusion: as per local guidelines for monoclonal antibodies, with a minimum as follows for each infusion of PF-07901801 and tafasitamab.           
 
PF-07901801: C1D1: pre (within 15 min prior), EOI (±15 min), (end of): 2h (±15 min). ≥C1D8: pre and EOI (±15 min).
 
Tafasitamab: pre, 15 (±5), 30 (±10), and then every 60 (±15) minutes during infusion and at EOI (± 20 min). After 3 infusions: pre and EOI (±15 min).
 
 
 
See Section 8.3.2 for additional information.
 

12-Lead ECG	X	X					X			X		X	X				
 
C1D1, C2D1, C3D1: Pre-PF-07901801 dose, PF-07901801 EOI (window for EOI: +30 min).
 
C4D1, C5D1, C6D1: pre PF-07901801 dose
 
See Section 8.3.3 for additional information.
 

B-symptoms	X	X					X			X		X					
 
See Section 8.3.6.
 

ECOG assessment	X																
 
Per Appendix 13.
 

PFIZER CONFIDENTIAL

CT02-GSOP Oncology Clinical Protocol Template (01 April 2022)

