##### 9.4.5.1. Electrocardiogram Analyses

Changes from baseline for the ECG parameters QT interval, heart rate, QTcF interval, PR interval, and QRS complex will be summarized by dose level and time.

The number (%) of participants with maximum post-dose QTcF values and maximum increases from baseline in the following categories will be tabulated by treatment:

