##### Safety QTcF Assessment

Degree of Prolongation	Mild (ms)	Moderate (ms)	Severe (ms)
Absolute value	>450-480	>480-500	>500
Increase from baseline		30-60	>60

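### SAP 6.7.6 contradicts itself and Protocol 9.4.5.1 on which ECGs enter the QTcF prolongation counts; under its pre-dose restriction the counts can be too low

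*SAP*

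**What the plan says.** **Protocol 9.4.5.1** plans a categorical table: "The number (%) of participants with maximum post-dose QTcF values and maximum increases from baseline in the following categories", by treatment. The categories, under the title "Safety QTcF Assessment", are absolute values of >450-480, >480-500 and >500 ms, and increases of 30-60 and >60 ms. It does not limit which post-dose ECGs count.

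**Protocol Table 1 (Schedule of Activities), 12-lead ECG row**, schedules both pre-dose and EOI ECGs in the first three cycles: "C1D1, C2D1, C3D1: Pre-PF-07901801 dose, PF-07901801 EOI (window for EOI: +30 min". At C4D1, C5D1 and C6D1 the notes name a pre-dose ECG only.

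**SAP 6.7.6** makes four statements that bear on the point:
- Its first sentence takes all on-treatment ECG assessments into the ECG summaries.
- The lead-in under 'ECG Summaries' restricts the analyses listed beneath it: "by treatment group, during the on-treatment period, for pre-PF-07901801 ECG records". These are the by-visit descriptive statistics and the notable-value frequencies, with cut-offs "QT/QTcF increase from baseline > 30 ms, > 60 ms" and "QT/QTc > 450 ms, > 480 ms, > 500 ms". For percentages, "The denominator to calculate percentages for each category is the number of patients evaluable for the category".
- Changes from pre-infusion to EOI are summarised separately for the first three cycles, and notable values are listed by patient and time point.
- Unscheduled ECGs stay out of the by-visit change statistics. "However, they will be used in the analysis of notable ECG changes and the shift table analysis of notable QT parameters".

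**SAP 2.1**, the place for departures from the protocol's analyses, is marked as not applicable.

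**The concern.** The protocol's table is meant to show how far QTcF rose in each participant at any time after dosing. The EOI ECGs are the only scheduled dosing-day ECGs taken just after a PF-07901801 infusion. If the SAP lead-in is followed, a participant who crosses a cut-off only at a scheduled EOI ECG is listed but not counted. An unscheduled post-dose ECG with the same value would be counted under the last sentence of the section.

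The cut-offs have a use outside the table. Protocol Appendix 8 treats a new QTcF above 480 ms, or a rise of at least 60 ms, as a possible AE, and a QTcF above 500 ms as a possible SAE. At stake is a possible undercount in a descriptive safety table. No estimand, decision rule or dose-escalation step depends on it.

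**Working it through.** The documents state no figure on this point, so there is none to reproduce. The check sets the texts side by side and counts the scheduled records.

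**1. Which records may enter the counts?**

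| Source | Records admitted |
|---|---|
| Protocol 9.4.5.1 | Any post-dose ECG; the participant's maximum is used |
| SAP 6.7.6, first sentence | All on-treatment ECGs |
| SAP 6.7.6, lead-in | Pre-PF-07901801 records only |
| SAP 6.7.6, last paragraph | Unscheduled ECGs also used for notable changes |

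The first sentence and the lead-in cannot both hold for the notable-value counts. The lead-in is the more specific text and stands directly above those counts, so a programmer would probably follow it. The last paragraph restores unscheduled ECGs but not scheduled EOI ECGs.

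**2. Direction of the effect.** For one participant, the maximum over a subset of ECGs cannot exceed the maximum over all of them. So for each cumulative cut-off, the number of participants above it under the restriction is less than or equal to the number without it. The denominator can change as well, because it counts only evaluable patients and the SAP does not say what makes a patient evaluable. The statement about direction therefore concerns counts, not percentages.

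**3. Share of scheduled records removed.** Inputs are the ECG notes in Table 1.
- C1D1 to C3D1, pre-dose and EOI: 3 × 2 = 6
- C4D1 to C6D1, pre-dose only: 3 × 1 = 3
- Total through Cycle 6: 6 + 3 = 9, of which 6 are pre-dose and 3 are EOI

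Assumption A: the C1D1 pre-infusion ECG is taken before lenalidomide and is the baseline. Then 9 − 1 = 8 records follow it, 5 pre-dose and 3 EOI. The restriction removes 3/8 = 37.5%.

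Assumption B: that ECG is taken after lenalidomide. SAP 3.4 puts the safety baseline before the first dose of any study drug, so the ECG becomes a later record. The restriction then removes 3/9 = 33.3%.

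The documents do not settle which applies. Protocol 6.1.1.3 places lenalidomide before the PF-07901801 infusion on C1D1, and Table 1 times the ECG only relative to PF-07901801.

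EOT and follow-up ECGs are left out of this count. The columns of Table 1 are broken in the text. An ECG after the last infusion is not, read literally, a pre-infusion record. The follow-up visit at 28-35 days also falls mostly outside the SAP 5.2.7 window, which ends no later than 28 days after the last dose.

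**4. Cut-offs.** A participant has some value above X exactly when the maximum is above X. The protocol's absolute bands therefore follow from cumulative QTcF counts:
- n(>450) − n(>480) gives >450-480 ms
- n(>480) − n(>500) gives >480-500 ms

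For increases, n(>30) − n(>60) gives the protocol's 30-60 ms category except for an increase of exactly 30 ms. The SAP label for absolute values says QT/QTc and does not name QTcF.

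**The case against.** The strongest reply is that the first sentence of SAP 6.7.6 already admits all on-treatment ECGs, so EOI records may be meant to count. This stands in part. It rules out saying that the SAP definitely excludes them. It does not resolve the matter, because the lead-in says otherwise at the point where the counts are defined.

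A second reply is that EOI data are not lost. They are listed by patient and time point, and the change to EOI is summarised for cycles 1-3. With about 20 participants planned for Phase 1b and Phase 2 not initiated, a reader could count crossings from the listing. This stands as mitigation. But a change from pre-infusion to EOI is not a count against absolute cut-offs, and after C1D1 it is not a change from study baseline.

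A third reply is that Protocol 9 lets the SAP modify outlined analyses, and that ECG is neither a primary nor a secondary endpoint. Both are true, and both support a low severity. They do not explain why SAP 2.1 declares nothing.

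Three stronger readings are tempting and not supported:
- A reader might take 3 of 8 as a share of participants misclassified. It counts scheduled records, and the documents give no basis for the number of participants.
- A reader might infer that anyone who stops before C2D1 has no scheduled Day 1 ECG left for the counts. That holds only under assumption A.
- A reader might see the different categories as a substantive conflict. Apart from the QTcF label and the value of exactly 30 ms, they carry the same information.

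**Conclusion.** The inconsistency is real, and minor. SAP 6.7.6 gives two incompatible rules for the notable-value counts. Under the more specific one, the scheduled EOI ECGs at C1D1, C2D1 and C3D1 are left out, and the table does not deliver the maximum post-dose QTcF and maximum increase of Protocol 9.4.5.1. Counts against each cut-off can be too low and, on these records, cannot be too high.

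The size in participants is unknown and may be zero. For scale, one participant is 1/20 = 5 percentage points of the roughly 20 planned for Phase 1b. The share would be larger within a dose level, but those sizes are not given. The record share of 3 of 8 rests on the C1D1 pre-infusion ECG being the baseline. Amendment 2 cancels Phase 2 but keeps Protocol 9.4.5.1, so the Phase 1b table is still planned.

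**What to change.** In SAP 6.7.6:
- Remove the pre-PF-07901801 restriction from the notable-value analysis. Base the counts on each participant's maximum QTcF and maximum increase from baseline over all on-treatment ECGs after the first dose of study treatment: pre-dose, EOI and unscheduled.
- State what makes a participant evaluable, for example a baseline and at least one such ECG.
- Name QTcF in the cut-offs and report the Protocol 9.4.5.1 bands. This is a small gain, for the reason given in step 4 of the working.
- The pre-dose limit may stay for the by-visit descriptive statistics if it is stated there, with the first sentence of the section reworded to agree.

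If the limit on the counts is intended, declare it in SAP 2.1 with the reason.

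The cost is SAP wording and one ECG table program. The ECGs are already scheduled, so no new data are needed. The downside for the sponsor is that reported prolongation counts may rise.
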